- 3. Individuals with a history of any dermatological disease or condition, including but not limited to active atopic dermatitis, psoriasis, eczema, active seasonal allergies, collagen diseases, or skin cancer involving the treated sites within the past 6 months
- 4. Cutaneous marks on the experimental area which could interfere with the assessment of skin reactions (pigmentation problems, scar elements, over-developed pilosity, ephelides, and nevi in too great quantity, sunburn, beauty spots, freckles, etc.)
- 5. Participants with asymmetric photodamage on dorsal hands due to environmental exposures (i.e., golfing) and/or other skin lesions including burns or scars resulting in significant skin surface variability between dorsal hands
- 6. Eczematous reaction still visible, scar, or pigmentary sequelae of previous tests on the experimental area
- 7. Allergy to colophony or nickel.
- 8. Allergy or reactivity to drugs, food or cosmetic products previously observed, including perfumes or cologne products.
- 9. Skin hyper-reactivity.
- 10. Forecast of intensive sun, tanning bed use or UV phototherapy during the test period.
- 11. Treatment with prescription-strength Vitamin A acid or its derivatives within 3 months before the beginning of the study.
- 12. Treatment with topical steroids on the experimental area within 16 days before the study.

Study constraints:

- 1. No application of products on the experimental area (except the suggested ones), particularly any antiaging cosmetic products except for sunscreen.
- 2. No change in hygiene habits
- 3. No application of any cosmetic moisturizing products on the face or any makeup on face and lips, on the day of study evaluations
- 4. No change in the way of life or in the physical activity

5. No change in dietary activities, or any treatment that significantly impacts body weight

Effective: 9/20/2017

- 6. No exfoliating treatment on the experimental areas
- 7. Description of any treatment undertaken during the study and all eventual deviations

Review of medical records, images, specimens					
Check all that apply (data includes medical records, images, specimens).					
Only data that exists before the IRB submission date will be collected.					
Date Range for Specimens and/or Review of Medical Records: Examples: 01/01/1999 through 12/31/2015, or all records through mm/dd/yyyy.					
Note: The Date Range must include the period for collection of baseline data, as well as follow-up data, if applicable.					

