 The study involves data that exist at the time of IRB submission and data that will be generated after IRB submission. Include this activity in the Methods section. Examples The study plans to conduct a retrospective chart review and ask subjects to complete a questionnaire. The study plans to include subjects previously diagnosed with a specific disease and add newly diagnosed subjects in the future. 					
The study will use data that have been collected under another IRB protocol. Include in the Methods section and enter the IRB number from which the research material will be obtained. When appropriate, note when subjects have provided consent for future use of their data and/or specimens as described in this protocol.					
Enter one IRB number per line, add more lines as needed					
Data Specimens Data & Specimens					
☐ Data ☐ Specimens ☐ Data & Specimens					
☐ Data ☐ Specimens ☐ Data & Specimens					
Data Analysis					

Power analyses may not be appropriate if this is a feasibility or pilot study, but end-point analysis plans are always appropriate even if only exploratory. Provide all information requested below, or provide justification if not including all of the information.

Data Analysis Plan:

All continuous data will be analyzed using independent 2-group t tests and reported as means \pm standard deviations. Categorical data will be compared between the 2 groups using chi-square tests and reported as counts and percentages. Nonparametric equivalents Wilcoxon rank-sum and Fisher exact tests will be used as needed for nonnormal distributions and low variable numbers, respectively. Treatment effects on outcomes will be compared between baseline versus HPE and HPE versus market competitor group with a significance level of p < 0.05.

Endpoints

Primary:

Evaluation of the tolerability of the study product.

- a. Nature, incidence, and severity of adverse events (AEs)
 - 1) Defined as any untoward or undesirable medical occurrence in the form of signs, symptoms, abnormal findings, or diseases that emerge or worsen relative to baseline (i.e., if present upon study entry) during the study regardless of causal relationship.
 - 2) Assessment
 - i. Incidence and severity of AEs (mild, moderate, severe)
 - ii. Relationship of AEs to study product (probable, possible, unlikely, unrelated)
 - 1. If possibly or probably related to the study product, determine whether related to the product itself or procedures pertaining to delivery of the study product.

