 - iii. Incidence of serious adverse events (SAEs) defined as AEs that result in death, life threatening adverse experiences, hospitalization, new or prolonged disability/incapacity, persistent or significant congenital defect/anomaly, or other events that in the opinion of the PI may have adversely affected the rights, safety, or welfare of the subjects or others, or substantially compromised the research data.
 - 3) Methods
 - i. Spontaneous subject reports
 - ii. Subject interview by study personnel
 - iii. Clinical examination during face-to-face clinic follow-ups
 - 4) Timing
 - i. Baseline
 - ii. 6-week post-treatment (acute)
 - iii. 12, 26- and 52-weeks post-treatment (delayed)

Change in photoaging scores from Baseline at 6,12, 26- and 52-weeks.

a. Canfield VISIA CR Gen 5 with 3DPrimos will be used to evaluate qualitatively and quantitatively skin profile changes (color evenness and roughness measurements), and to assess wrinkle count, depth, and volume by a full-aligned facial and bilateral dorsal hands images.

Information about Canfield VISIA CR is a high-resolution clinical imaging system (21 Megapixel resolution 45MP Canon EOS R5) which uses LED lighting. No radiation-based exposure. It captures high-resolution

photographic images. More information on prior model (without 3D Primos): https://www.canfieldsci.com/common/docs/products/1/brochures/VISIACRBrochure.pdf

Secondary:

- 1) Dermatopathologic evaluation of the skin
 - a) Skin microbiome: To define skin facial microbial clades, a standard swab and tape stripping method will be used on all interested subjects. Both methods are minimally invasive and can yield optimal results. All subjects will be offered skin microbiome analysis unless they did not meet criteria (i.e., washed face 3-hours prior to clinical visit, which would shift the skin microbiome; or prior allergy to adhesives) or unless they decline
 - i) Skin microbiome: Skin swab collection (n=80)
 Skin bacteria will be collected by the swabbing method as described in previous studies [4]. In brief, the left and right malar cheeks will be gently swabbed with a single dry cotton swab in a Z-stroke manner [5]. For skin microbiome, the swab head will be stored in a sterile 1.5-mL centrifugation tube at -80°C until ready for analysis.
 - ii) Skin microbiome: Tape-stripping collection (n=80)

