Additionally, Canfield shall take all appropriate technical and organizational measures which are necessary to prevent the unauthorized or unlawful processing of, the unauthorized or unlawful disclosure of and/or the accidental loss or destruction of, or damage to, such data, including without limitation, implementation and enforcement of administrative, technical and physical security policies and procedures. Incident Reporting. Canfield shall promptly notify Sponsor in the event of a security breach or incident involving any data which Canfield is processing on behalf of Sponsor.

Study procedures

The skin biopsies, skin swabs and long-term follow-up visits will be obtained separately from 80 subjects.

- n=80 subjects
- Entire face and decolletage HPE (n=80)
- HPE (n=80) to be applied on the right dorsal hand
- Skinceuticals CE Ferulic (n=80) to be applied on the left dorsal hand
- Skin biopsy (baseline): Left upper inner arm untreated (n=30)
- Skin biopsy (week 12): Right upper inner arm HPE treated (n=30, same subjects as above)
- Microbiome analysis (baseline): Left and right malar cheek untreated (n=80 with both skin swab and tape-stripping method)
- Microbiome analysis (week 12): Left and right malar cheek HPE treated (n=80 with both skin swab and tape-stripping method)

N=30 - Skin biopsy: Two total skin biopsies will be performed per subject (n=30 subjects). In this study, we will remove a small piece of skin from untreated skin on the left upper inner arm (baseline) and HPE treated area on the right upper inner arm (week 12). This is called a skin biopsy.

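### The HPE-versus-competitor contrast compares two hands of one person but is planned as an independent-groups test; it needs a paired change with a 95% CI, with baseline adjustment only as a sensitivity analysis while the side is fixed

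*Combined protocol and SAP*

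**What the plan says.** The second primary endpoint (Endpoints, Primary) is "Change in photoaging scores from Baseline at 6,12, 26- and 52-weeks", measured on "full-aligned facial and bilateral dorsal hands images". Under Study procedures the allocation is "HPE (n=80) to be applied on the right dorsal hand" and "Skinceuticals CE Ferulic (n=80) to be applied on the left dorsal hand". Randomisation of the side is not mentioned. The hands are the only site that receives the competitor, so the aim of comparing the two products rests on them alone.

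Figure 1 lists left-hand imaging at weeks 0, 6 and 12. The Visit 2 text continues HPE after week 12 on the face and decolletage only. The hand contrast therefore has a baseline and two follow-up times.

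On analysis, the Data Analysis Plan states "All continuous data will be analyzed using independent 2-group t tests and reported as means" with standard deviations, and "Treatment effects on outcomes will be compared between baseline versus HPE and HPE versus market competitor group" at p < 0.05. The stated non-parametric fallback, the Wilcoxon rank-sum test, is also an independent-samples test. The plan names no paired analysis, baseline covariate or confidence interval, and does not say whether the hand test uses changes or raw follow-up values. It gives no power, SD or correlation.

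Exclusion 5 removes subjects with asymmetric photodamage or lesions "resulting in significant skin surface variability between dorsal hands", without a numeric limit.

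**The concern.** Each subject serves as his or her own control, but the named test treats 80 right hands and 80 left hands as 160 unrelated units. The two hands share age, skin type, sun history, season, camera session and adherence, so their changes are likely to be positively correlated. An independent-groups standard error leaves that correlation in the error term, and the only competitor comparison becomes less sensitive than the data allow.

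The reporting adds to this. Separate means and SDs for the two hands do not let a reader recover the precision of the within-person difference. With no interval, margin or power statement, a p-value above 0.05 could be read as showing that the products are alike.

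There is a further question about baseline. A change score subtracts the whole baseline right-left difference, including its measurement noise. A regression on that difference can be more precise, but whether it is safe depends on how the hands were allocated.

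**Working it through.** The plan states no sample-size or precision figure, so there is nothing of its own to reproduce. Taken from the documents: n = 80, fixed sides, both hands imaged at baseline, significance level 0.05. Assumed: two-sided testing, 80 complete pairs, equal SDs across hands and visits, and every correlation and asymmetry below.

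**Step 1. Independent versus paired.** Let s be the SD of one hand's change and c the correlation between the two hands' changes.
- Independent-groups SE = s√(2/80) = 0.158 s.
- Correct SE of the mean right-minus-left change = s√(2(1−c)/80).
- Ratio = 1/√(1−c).

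| c (assumed) | Correct SE | Independent SE / correct SE | Actual two-sided type I error, 2[1 − Φ(1.96/√(1−c))] | Independent-test power where the paired test has 80%, Φ(2.80√(1−c) − 1.96) |
|---|---|---|---|---|
| 0.3 | 0.132 s | 1.20 | 0.019 | 0.65 |
| 0.5 | 0.112 s | 1.41 | 0.006 | 0.51 |
| 0.7 | 0.087 s | 1.83 | 0.0003 | 0.34 |

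Here 2.80 = 1.96 + 0.84. With positive correlation the planned test is too conservative, and power is lost.

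**Step 2. Paired change versus baseline-adjusted difference, no expected asymmetry.** Let D0 and D1 be the right-left differences at week 0 and at follow-up, with common SD σ and correlation ρ.
- Paired change: mean(D1 − D0), variance 2σ²(1−ρ)/n.
- Adjusted: intercept of D1 on D0 at D0 = 0, variance about σ²(1−ρ²)/n.
- Variance ratio = (1−ρ²)/[2(1−ρ)] = (1+ρ)/2.

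| ρ (assumed) | Variance ratio | SE ratio | Detectable difference at 80% power, paired → adjusted |
|---|---|---|---|
| 0.2 | 0.60 | 0.775 | 0.396σ → 0.307σ |
| 0.5 | 0.75 | 0.866 | 0.313σ → 0.271σ |
| 0.8 | 0.90 | 0.949 | 0.198σ → 0.188σ |
| 0.9 | 0.95 | 0.975 | 0.140σ → 0.137σ |

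Simulation at n = 80 agrees (variance ratios 0.61, 0.77 and 0.91 at ρ = 0.2, 0.5 and 0.8).

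**Step 3. The same comparison with a stable asymmetry.** Suppose the expected right-left difference is μ at both visits and the products do not differ. The paired change has expectation μ − μ = 0. The intercept has expectation μ − ρμ = (1−ρ)μ, which would be read as a product effect.

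Simulated two-sided type I error at μ = 0.2σ (20,000 replicates, n = 80):

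| ρ | Adjusted | Paired change |
|---|---|---|
| 0.3 | 0.248 | 0.053 |
| 0.5 | 0.168 | 0.050 |
| 0.7 | 0.107 | 0.049 |
| 0.9 | 0.066 | 0.050 |

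**Step 4. Break-even.** The adjusted estimate has the larger mean squared error when (1−ρ)²μ² exceeds the variance it saves. That saving is σ²[2(1−ρ) − (1−ρ²)]/n = σ²(1−ρ)²/n. The factor (1−ρ)² cancels, leaving |μ| > σ/√80 = 0.11σ whatever ρ is. At ρ = 0.5 the simulated root mean squared error is 0.097σ adjusted against 0.111σ paired when μ = 0, and 0.141σ against 0.112σ when μ = 0.2σ.

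**The case against.** The strongest counter-argument is that choosing between two within-person estimators is second-order and that the planned test errs on the safe side. With positive correlation it does: Step 1 shows fewer false positives than nominal. That does not rescue it. The cost falls on power, and an insensitive test with no interval is the setting in which a null result gets misread as similarity.

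A reader might also infer that adjusting for the week-0 right-left difference gives a tighter estimate for free and should lead, because Exclusion 5 leaves only measurement noise at baseline. The documents do not support this. The exclusion is a clinical screen with no numeric limit, and it cannot be relied on to hold a systematic asymmetry, for example from handedness or habitual sun exposure, below 0.11σ. Randomising the side would make the expected difference zero, but here side and product are fully confounded. Nor does the premise fit the more favourable precision figures: if the baseline difference were only visit-specific noise, ρ would be near zero, whereas ρ = 0.5 under equal variances means half of the variance is stable asymmetry.

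Two parts of the case for adjustment stand. It is more precise when μ = 0, and it is the better choice if an observed baseline gap is pure noise. That is enough to show it, but not to make it the main analysis. Neither estimator corrects a difference between sides that develops over time.

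**Conclusion.** The concern holds for the test and the reporting. The plan names an independent-groups test for a within-person contrast and asks for summaries that do not show its precision. The standard error is overstated by a factor of about 1.2 to 1.8 if the hands' changes correlate at 0.3 to 0.7; the factor is 1 only if they are uncorrelated. Those correlations are assumptions.

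The gain from baseline adjustment is conditional. Its SE is 2.5% to 22.5% smaller for assumed ρ of 0.9 down to 0.2 if μ = 0, but it is biased by (1−ρ)μ otherwise. With HPE fixed to the right hand, the paired change should lead.

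A reader might infer that the planned test inflates false-positive findings. With positively correlated hands it does the reverse.

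**What to change.** Add to the Data Analysis Plan, for each hand measure at weeks 6 and 12:

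1. **Main analysis while HPE stays on the right hand.** Compute one right-minus-left change from baseline per subject. Report its mean with a 95% CI and a paired test. If a non-parametric fallback is kept, use the signed-rank test on these differences.
2. **Sensitivity analysis.** Regress the follow-up right-left difference on the week-0 right-left difference, one row per subject, and report the intercept with its 95% CI. State that it is evaluated at a baseline difference of zero: centring at the sample mean would return the plain follow-up difference and remove no baseline asymmetry.
3. **Order.** The adjusted estimate becomes the main one only if the side is randomised per subject.
4. **Interpretation.** State that a non-significant difference will not be reported as equivalence.

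The cost is a short addition to the plan and one regression per measure and visit, with no new data. The downside is two related estimates to present.

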The site(s) or area of the skin identified for skin biopsy will be cleaned with antiseptic and may be numbed by injecting a small amount of numbing medicine, through a small needle. Some people (fewer than 1 in 10,000) are allergic to the shot you will get to numb the area where the skin is taken. The biopsy procedure is conducted by taking a larger circular tool or needle (about 1/5th of an inch in diameter), inserting it into the skin and removing the core piece that fits inside the circle. There could be bleeding from the site, and this might require placement of a stitch. Heavy bleeding from a skin biopsy is rare. Other complications could include pain, and there is the possibility of the biopsy site becoming infected. Skin biopsies cause infections about 10% of the time. A small scar will form at the biopsy site. The scar is usually much smaller than the original biopsy. The procedure is conducted using sterile instruments after disinfectant or antiseptic cleaning of the skin.

N=80 - Skin swab or Tape-stripping: Method validation will be performed at baseline visit. All subjects will be evaluated by skin swab method and tape stripping method at baseline visit. All 80 subjects will receive the skin swab method and tape stripping method at week 12 visit for microbiome analysis post-HPE treatment. All subjects will be offered skin microbiome analysis unless they did not meet criteria (i.e., washed face 3-hours prior to clinical visit, which would shift the skin microbiome; or prior allergy to adhesives) or unless they decline

In this study, bacteria will be collected by either of two methods (standard swab and tape stripping method) from your skin to culture the bacteria that normally live on the skin.

Standard swab: we will gently rub a Q-tip like swab on your skin around 4-5 times to obtain the sample.

Tape-stripping: we will use 2 specialized, transparent, adhesive disks, maintained on the skin for 1 minute to obtain the samples. You will be instructed to avoid contact with water and soap at least 3 hours prior to sample collection and refrain from wearing make-up on the day of sample collection.

Video Interview

Participants will also be asked if they would like to be part of a video interview to talk about their experience in the study and with the products.

Screening Visit / Baseline Visit (Visit 0)

The screening visit will take place prior to enrollment to determine if the potential subject is eligible to participate in the study.

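### Microbiome endpoint: the only analysis rule is an unpaired test on paired cheek samples, with no multiplicity control, no lead sampling method and no stated readout

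*Combined protocol and SAP*

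**What the plan says.** The Data Analysis Plan is the only analysis text in the combined protocol and SAP. It states "All continuous data will be analyzed using independent 2-group t tests". For other data types it adds "Categorical data will be compared between the 2 groups using chi-square tests" and "Nonparametric equivalents Wilcoxon rank-sum and Fisher exact tests will be used as needed for nonnormal distributions and low variable numbers, respectively". The comparisons named are baseline versus HPE and "HPE versus market competitor group with a significance level of p < 0.05". The text contains no paired test and no multiplicity adjustment.

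Under Endpoints, Secondary, the skin microbiome item describes the sampling: "To define skin facial microbial clades, a standard swab and tape stripping method will be used on all interested subjects". It gives no summary measure, taxonomic level or number of clades.

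Study procedures lists left and right malar cheek samples, untreated at baseline and HPE-treated at week 12, by both methods with n=80. It says "Method validation will be performed at baseline visit" but gives no agreement statistic or decision rule. It then says "All 80 subjects will receive the skin swab method and tape stripping method at week 12 visit for microbiome analysis post-HPE treatment". The only laboratory readout mentioned there is culture. The 2X concentration substudy repeats swab and tape at both visits in 50 more subjects.

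**The concern.** Each subject serves as their own baseline, but the rule treats the two visits as two independent groups. It therefore discards the within-subject correlation and uses too large a standard error for the change. A finding of no shift would be weak evidence that the facial microbiome was preserved.

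The endpoint is also stated as clades, in the plural, and measured by two methods. Every clade can be tested twice at p < 0.05, and nothing prevents the more striking of the two results from being quoted. The baseline comparison of swab with tape looks like the natural means of choosing between them, but no choice follows from it.

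Finally, the readout is not stated. If it is relative abundance, the clade values in a sample sum to one, so a true rise in a dominant clade pushes the others down. Tests on raw proportions would then count unchanged clades as findings.

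**Working it through.** The plan gives no power, effect size or error rate for this endpoint, so there is no figure of its own to reproduce.

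**Inputs.** From the documents: nominal alpha 0.05 (taken as two-sided; the plan does not say), independent tests, the same subjects and cheeks at both visits, two methods, n=80. Assumed: within-subject correlation r of 0.3, 0.5 or 0.7; 50 to 100 clades per method; independent tests; equal variances; large-sample normal approximation.

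**1. True size of the unpaired test.** With n pairs and variance s², the variance of the mean change is 2s²(1−r)/n. The independent test uses 2s²/n. The unpaired statistic is therefore the paired one multiplied by √(1−r), and it rejects only when the paired statistic exceeds 1.96/√(1−r). Size = 2[1 − Φ(1.96/√(1−r))].

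**2. Power.** Take a shift that a paired test detects with 80% power: its standardised size is 1.96 + 0.84 = 2.80. The unpaired test detects it with power Φ(2.80 − 1.96/√(1−r)).

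| r | Effective cut-off | Size per test | Power (paired = 80%) |
|---|---|---|---|
| 0.3 | 2.343 | 0.019 | 68% |
| 0.5 | 2.772 | 0.0056 | 51% |
| 0.7 | 3.578 | 0.00035 | 22% |

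**3. Chance of at least one false clade when nothing changes.** This is 1 − (1 − size)^K for K independent tests.

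| r | One method, K = 50 to 100 | Both methods, K = 100 to 200 |
|---|---|---|
| 0.3 | 62% to 86% | 86% to 98% |
| 0.5 | 24% to 43% | 43% to 67% |
| 0.7 | 2% to 3% | 3% to 7% |

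At r = 0.5 the expected number of false clades per method is 50 × 0.0056 = 0.28 to 100 × 0.0056 = 0.56. Swab and tape results are probably correlated, so the last column is at the upper end.

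**4. Relative abundance, if that is the readout.** This was simulated with 80 pairs, log-normal clades (log SD 1) closed to proportions, 20 or 50 clades, a dominant clade holding about 0.2 to 0.35 of the total, and 200 runs per scenario. All of these settings except the 80 pairs are assumptions.

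- No true change, r = 0.5: unpaired tests on proportions reject in about 0.6% to 1.1% of tests. Closure alone does not inflate error.
- Dominant clade shifted by ±0.7 on the log scale, r = 0.5: unchanged clades are flagged in 7% to 26% of tests (20 clades) or 3% to 11% (50 clades). At least one is flagged in 76% to nearly 100% of runs. At r = 0.8 the range is 18% to 92%.
- Same shift, r = 0.5, paired tests on centred log-ratios with Benjamini-Hochberg: at least one unchanged clade is flagged in 4% to 16% of runs. Over all correlations tried, the range is about 4% to 23%.

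**The case against.** A reader might infer that the planned tests will report false microbiome shifts, with a 92% to 99% chance of at least one (1 − 0.95^50 to 1 − 0.95^100). The documents do not support that. The figure needs tests that truly operate at 5%, and the independent tests specified do not do so on positively correlated pairs. When nothing changes, the likelier cost of the rule as written is missed shifts.

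A reader might also take the data to be compositional. That is an inference: sequencing and relative abundance are never mentioned, and the only stated readout is culture, in lay wording. Culture counts need not sum to one, and presence or absence would go to chi-square or Fisher tests instead. Those are also unpaired, so the main defect survives. Even with relative abundances, spurious flags beyond chance require a dominant clade that truly moves. The community has then changed, and the error lies in which clades are named.

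It is fair to add that this is a descriptive secondary item outside the stated aims, and that the unpaired rule and missing multiplicity control affect other endpoints too. A better test also cannot attribute a change to HPE: the whole face is treated, no untreated or comparator cheek is sampled, and every kit includes cleanser, soap, sunscreen and moisturizer. These points limit the consequence. They do not make an independent-groups test suitable for paired samples, nor supply a lead method.

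**Conclusion.** The concern holds as a defect of specification and choice of test. That the data are paired, that the stated tests are independent, and that there is no multiplicity rule, lead method or defined readout all follow from the documents without assumption.

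The size depends on quantities the plan does not give. At an assumed correlation of 0.5, per-test size is about 0.6% and power falls from 80% to about 51%. The chance of at least one false clade is about 24% to 43% per method for 50 to 100 independent clades. Lower correlation moves the problem towards false calls, and higher correlation towards lost power. The extra flagging of unchanged clades applies only if the readout is relative abundance and a dominant clade truly shifts. The change should be made, but the primary endpoints do not depend on it.

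**What to change.** 1. State the laboratory readout and the taxonomic level.
2. Give an agreement statistic and a decision rule for the baseline swab-versus-tape comparison, and use it to name one lead method before any week-12 sample is analysed. Samples are stored at −80°C until analysis, so this is feasible. Report the other method as supportive.
3. Replace the independent tests with a paired analysis. Make one community-level within-subject test the microbiome endpoint, for example a distance-based permutation test with permutations restricted within subject.
4. Treat individual clades as exploratory, using paired tests with Benjamini-Hochberg control. Apply a log-ratio transformation only if the data are relative abundances. In the simulation this reduced spurious flags but did not hold them at 5%, so clade findings remain tentative.
5. Report any difference as a pre-post change, not as an effect attributable to HPE.

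The cost is SAP wording and standard software, with no change to visits or sampling. The downside is that fewer individual clades may be called significant.
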